8.4.2 Variables for Identifying Subpopulations

8.4.2.1 Adults Aged ≥ 65 Years and Other Age Groups

Participants will record their age at enrolment and will be categorised accordingly.

8.4.2.2 Pregnant Women

At enrolment, females aged < 50 years will be asked the date of their last menstrual period and if they are currently pregnant. Those who have not reported pregnancy, will be prompted for this information at each safety follow-up. Women who report pregnancy will be asked for their expected due date. Their estimated date of conception will be calculated, and those vaccinated (either first or second dose) between 45 days prior to the estimated date of conception and, any other point during pregnancy, will be included in the pregnant women subpopulation.

8.4.2.3 Breastfeeding Women

At enrolment and at all safety follow-ups (except at 18 months), females aged < 50 years will be asked if they are currently breastfeeding. Participants who report they are breastfeeding when they receive either vaccine dose (first or second) will be included in the subpopulation.

8.4.2.4 Immunocompromised Participants and Participants with Autoimmune or Inflammatory Disorders

At enrolment, participants will be asked if they have ever been diagnosed with certain medical conditions and if they are currently taking an immunosuppressant medication. Study personnel will confirm medical conditions and immunosuppressant medications with medical records. Confirmed medical conditions and medications will be used to categorise participants as immunocompromised and/or as having an autoimmune or inflammatory disorder.

The subpopulation of immunocompromised participants will include participants taking an immunosuppressant (eg, tracrolimus, cyclosporine, corticosteroids, and methotrexate), participants with a diagnosis of an autoimmune disease, neuroimmune condition, or another condition affecting the immune system, and participants currently taking medication for cancer or being treated for cancer.

The subpopulation of participants with an autoimmune or inflammatory disorder will include participants diagnosed with an autoimmune disease or neuroimmune condition.

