6.2 AZD1222 Background

SCI

Coronaviruses are enveloped viruses with positive-sense single-stranded RNA genomes. The spike glycoprotein is a coronavirus surface protein involved in receptor binding and mediating virus entry into host cells during infection (Li 2016). AZD1222 is a recombinant replication defective chimpanzee adenovirus expressing the severe acute respiratory syndrome coronavirus 2 (SARS-CoV-2) spike glycoprotein. Development of AZD1222 was initiated by the University of Oxford with subsequent transfer of development activities to the Sponsor.

The University of Oxford is investigating the safety, immunogenicity, and efficacy of AZD1222 in 4 ongoing controlled (meningococcal vaccine or placebo) clinical studies. A pooled, interim analysis of the 4 ongoing studies found AZD1222 to have an acceptable safety profile in adults following vaccination (Voysey et al 2021). The incidence of serious adverse events (SAEs) and adverse events of special interest (AESIs) was similar between the analysis groups (participants receiving AZD1222 vs controls) and all 4 of the non-COVID-19 deaths (1 in an AZD1222 recipient and 3 in control recipients) were considered unrelated to the study product (Voysey et al 2021). Local and systemic reactogenicity of AZD1222 was tolerable and decreased in incidence and severity in older adults and after the second dose (Voysey et al

2021). Common local symptoms have included injection-site pain and tenderness and common systemic symptoms have included fatigue and headache (Folegatti et al 2020, Ramasamy et al 2021, Barrett et al 2020).

In addition to the Oxford studies, the Sponsor has 3 ongoing clinical studies, including a Phase III double-blind placebo-controlled study. All clinical studies to date have enrolled participants \geq 18 years of age.

To date, there are no important identified risks for AZD1222. The important potential risks of AZD1222 are nervous system disorders (including immune-mediated neurological conditions), vaccine-associated enhanced disease (VAED) (including vaccine-associated enhanced respiratory disease [VAERD]), and anaphylaxis. Areas of missing information include use of AZD1222 during pregnancy and while breastfeeding, use in immunocompromised persons, use in frail persons with comorbidities, use in persons with autoimmune or inflammatory disorders, interactions with other vaccines, and long-term safety.

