^e Selected medical conditions: neuroimmune condition, other neurological condition, bleeding disorder, asthma, chronic obstructive pulmonary disease, diabetes, cerebrovascular conditions, heart disease, other cardiovascular disease, chronic kidney disease cancer, autoimmune disease, solid organ transplant recipient, other condition affecting immune system, liver disease, history of allergic conditions, depression/anxiety, viral/bacterial infection leading to hospital admission, and other chronic condition or conditions for which participant received treatment or medication in last month. If a participant indicates having any of these conditions, the participant will be asked if they are currently taking any medication or being treated for it. Specific medication will not be asked unless the participant indicates they are taking an immunosuppressant.

^f Adverse event reports can be scheduled (timed follow-ups) or unscheduled. At the scheduled timepoints, participants will be asked if they've had any new or worsening health issue resulting in consultation with a medical doctor, an emergency room visit or hospitalisation, or a significant or long-term disability or incapacitation. When a participant responds "yes", the participant will be asked for more details. For reported COVID-19 cases, this will include patient-reported symptoms.

^g Healthcare providers will provide input and study personnel will assess the seriousness and causality of AEs.

h

CC

PASS Protocol AZD1222, D8111R00003

CI

- ⁱ Participants vaccinated with AZD1222 during pregnancy or up to 45 days before the estimated date of conception will be asked to follow outcomes in their child for up to 12 months after birth. Breastfeeding participants will also be asked to follow-up on their child's health. Before any request for a child's medical records, the participant will be asked for additional informed consent. The child's other parent may also be asked for consent, depending on local requirements.
- ^j Outcomes in infants will be requested up to 12 months of age. However, follow-up of pregnancy and infant outcomes will not be continued past 24 months post-first dose for the last participant enrolled in the study.

k CC

As a data source, participant means either the participant directly or the participant's designated proxy.

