Subgroup Analyses. Incidence rates and potential differences in the risk and pattern of participants experiencing AEs within different subgroups will be explored, including categories that are considered missing information at the start of the study. The subgroup analyses will include:

- Age at vaccination (18 to 34, 35 to 49, 50 to 64, 65 to 79, and \geq 80 years)
- Sex (male, female)
- Race/ethnicity
- Country (Germany, France, Spain, Sweden)
- Previous COVID-19 infection
- Pregnant/breastfeeding women
- Participants with immunodeficiency
- Participants with autoimmune or inflammatory disorders
- Frail participants with comorbidities (chronic obstructive pulmonary disease, diabetes, chronic neurological disease, or cardiovascular disorders)
- Participants who receive other vaccines in addition to AZD1222 (within 1 month)
- Number of AZD1222 doses received (1 dose, 2 doses)

Handling of Missing Data. No restrictions on the percentage of missingness will be made, but the baseline characteristics of the participants lost-to-follow-up will be tabulated. The differences between the baseline characteristics for the total group and the group lost-to-follow-up will be related to the subgroup analyses to assess for a possible impact on AE risk. Adjustment for missingness will be further specified in the statistical analysis plan but may include multiple imputation, joint modelling, and inverse probability weighting.

To deal with missingness due to death, death will be interpreted as a competing risk in the above analyses.

Mitigation of Potential Bias and Confounding. Strategies include:

- To account for possible sampling bias due to the recruitment of vulnerable populations first (residual confounding), in the risk assessment analyses, in addition to the expected background event rate, the rates will be multiplied by 1.2, 1.5, and 2.0 times, for example.
- Subgroup analyses within risk assessment analyses will also be performed, if feasible. When characteristics are found that both are related to differences in AE risk and to differences between study participants and the overall vaccinated population, weighting will be added.
- Additional sensitivity analyses will include:

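### The subgroup labelled autoimmune or inflammatory is defined by autoimmune and neuroimmune diagnoses, so the word inflammatory adds no criterion and the subgroup lies wholly inside the immunocompromised group

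*Protocol*

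**What the plan says.** Protocol 6.2 includes "use in persons with autoimmune or inflammatory disorders" among the areas of missing information. Section 8.3.2.2 names the same group as a subpopulation of interest. Section 8.8 lists "Participants with autoimmune or inflammatory disorders" among the subgroup analyses and says these cover categories that count as missing information at study start.

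The group is defined in 8.4.2.4. The basis is stated first: "Confirmed medical conditions and medications will be used to categorise participants as immunocompromised and/or as having an autoimmune or inflammatory disorder". The rule follows: "The subpopulation of participants with an autoimmune or inflammatory disorder will include participants diagnosed with an autoimmune disease or neuroimmune condition".

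The preceding paragraph of 8.4.2.4 defines the neighbouring group. It opens "The subpopulation of immunocompromised participants will include participants taking an immunosuppressant" and then adds people with an autoimmune disease, a neuroimmune condition or another condition affecting the immune system, and people under treatment for cancer.

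The conditions asked about at enrolment are in Table 3, footnote e. The list starts "Selected medical conditions: neuroimmune condition, other neurological condition, bleeding disorder, asthma, chronic obstructive pulmonary disease, diabetes", later has "autoimmune disease, solid organ transplant recipient, other condition affecting immune system, liver disease, history of allergic conditions", and ends with an open item: "other chronic condition or conditions for which participant received treatment or medication in last month". No item is named inflammatory disorder.

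**The concern.** The label has two parts and the rule serves one. A participant with a record-confirmed inflammatory disorder that is neither autoimmune nor neuroimmune meets no stated criterion for the subgroup that carries the name of that disorder.

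This matters because the subgroup exists to inform a declared gap in the safety knowledge of the vaccine. Followed as written, the study would report adverse event incidence under a heading that includes inflammatory disorders, from people selected without reference to them. A reader of the final report could take the gap as addressed when part of it was not studied.

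The rule also affects how two missing-information areas relate. Section 6.2 lists immunocompromised persons and persons with autoimmune or inflammatory disorders separately. Under 8.4.2.4 the second population adds nobody who is not already in the first.

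**Working it through.** The protocol states no figure on this point, so the check compares the label, the rule and the enrolment list.

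**Step 1: where each enrolment item leads under 8.4.2.4.**

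| Footnote e item | Immunocompromised group | Autoimmune or inflammatory group |
|---|---|---|
| Autoimmune disease | yes | yes |
| Neuroimmune condition | yes | yes |
| Other condition affecting the immune system | yes | not assigned |
| Cancer, under treatment | yes | not assigned |
| Other chronic condition (open item) | only if on an immunosuppressant | not assigned |
| Asthma, chronic obstructive pulmonary disease | only if on an immunosuppressant | not assigned |

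The items most likely to hold a non-autoimmune inflammatory disorder are the two catch-all items. One leads only to the immunocompromised group. The other leads to neither unless the participant takes an immunosuppressant.

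**Step 2: nesting.** Let A be the participants with an autoimmune or neuroimmune diagnosis. The autoimmune or inflammatory group is A. The immunocompromised group is A, plus those on an immunosuppressant, plus those with another immune condition, plus those under cancer treatment. A is therefore a subset of the immunocompromised group. An inflammatory criterion could bring in people outside it, for example a person with gout who takes no immunosuppressant.

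**Step 3: could it be repaired at analysis?** In part. Conditions entered under the catch-all items are on file, 8.5.4 has baseline comorbidities confirmed in medical records, and 10.4 has medical history coded in MedDRA. But Table 3 collects comorbidities at enrolment only, and records are described as confirming conditions, not as a search for unreported ones. What a participant did not report may not be recovered.

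**Step 4: illustration of size.** Only N = 15,000 (8.6, 8.8) comes from the protocol. The assumptions are that 3% to 8% have a qualifying diagnosis (a), that a further 1% to 5% have another inflammatory disorder (i), and that event risk is 4% in both groups and 2% in everyone else.

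- Capture of the labelled group = a / (a + i). Lowest: 450 / (450 + 750) = 37.5%. Middle (5% and 3%): 750 / (750 + 450) = 62.5%. Highest: 1,200 / (1,200 + 150) = 88.9%. Between 11% and about 62% would be missed.
- Precision of the subgroup estimate, 95% half-width = 1.96 × √(0.04 × 0.96 / n). With n = 750 it is 1.40 percentage points. With n = 1,200 (the middle case after widening) it is 1.11.
- If the analysis did compare the subgroup with everyone else, the event risk among the rest would be (0.04 i + 0.02 (N − a − i)) / (N − a). At 3% and 1% this is (6 + 288) / 14,550 = 2.02%, and a true risk ratio of 2.0 appears as 1.98. At 8% and 5% it is (30 + 261) / 13,800 = 2.11%, and the ratio appears as 1.90.

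Under these assumptions the effect lies in capture. Dilution of a contrast would be slight.

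**The case against.** The best case for leaving the text alone has five parts.

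- **The rule is not worded as exclusive.** Section 8.4.2.4 says who the group will include, whereas 8.4.2.5 writes an explicit restriction for the frail group. This carries some weight. But 8.4.2.4 uses the same verb for the immunocompromised group while allocating conditions one by one, and it gives the other-immune-condition item to that group and not to this one. As the only membership rule, it gives no ground for admitting anyone else.
- **The enrolment questions cannot be checked.** The participant questionnaires in Appendix C are not shown, and the autoimmune item may carry examples. That stands, and it makes a new checkbox optional. It does not alter the rule in 8.4.2.4, which classifies on confirmed diagnoses.
- **Some omitted participants are still analysed.** Those on corticosteroids or methotrexate enter the immunocompromised group. That stands too, but they do not appear in the group named after their disorder.
- **Details are left to the SAP.** Section 8.8 defers detailed methods, and the SAP is not at hand. Membership is not left open, however: the protocol fixes it, more narrowly than its own label.
- **The analysis is exploratory.** No primary result is affected, which limits the severity.

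A reader might infer that people with other inflammatory disorders are counted as unaffected, and so bias a comparison. The documents do not support this. Section 8.8 speaks of exploring rates and potential differences and defines neither a reference group nor an unaffected category. Nor should one infer that such disorders cannot be recorded: the catch-all items can hold them.

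**Conclusion.** The point stands as a mismatch between a label and its rule. The subgroup is named for autoimmune or inflammatory disorders in 6.2, 8.3.2.2 and 8.8, and its only definition admits autoimmune disease and neuroimmune condition. Other inflammatory disorders are not assigned to it, and it is wholly contained in the immunocompromised group as 8.4.2.4 defines that group.

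The harm is incomplete capture and a mislabelled result for a stated missing-information area. Its size cannot be derived from the documents. The capture range of about 38% to 89% rests entirely on assumed prevalences and only shows that the shortfall could be anything from modest to large. The mismatch itself depends on no assumption. Bias in a comparison forms no part of this conclusion. The point deserves correction before enrolment starts but does not touch the primary analysis.

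**What to change.** Amend the 8.4.2.4 rule to read *autoimmune disease, neuroimmune condition or other inflammatory disorder, confirmed in medical records*. State that MedDRA-coded, record-confirmed diagnoses entered under either catch-all item in footnote e can qualify. Optionally, add a matching item with examples to the footnote e list, which would reduce reliance on what participants volunteer. Report the autoimmune or neuroimmune stratum and the other inflammatory stratum separately.

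If the narrow group is what the sponsor intends, relabel it in 8.3.2.2, 8.4.2.4 and 8.8, and state that other inflammatory disorders remain unaddressed by this study.

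The cost is one clause in the definition, a coding rule and, if chosen, one questionnaire item. The downside is a somewhat more heterogeneous subgroup, which the separate strata make visible.

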8.4.2.5 Frail Participants with Comorbidities

The EMA's reflection paper on physical frailty has defined the concept of frailty "as a state of increased vulnerability resulting from aging and often disease associated decline ... leading to increased risk of adverse health outcomes..." (EMA 2015).

For this study, physical frailty will be identified at baseline using participant answers to the enrolment questionnaire as well as to the CCI

CCI

. Comorbidities will be

reported by participants at enrolment and then confirmed by study personnel through medical record reviews.

Only participants with physical frailty and comorbidities at baseline will be included in this subpopulation.

8.4.3 Outcome Measures

8.4.3.1 Adverse Events

The collection and analysis of AEs will focus on 3 categories of events:

- Serious adverse events
- Adverse events of special interest
- Medically-attended AEFIs

The following variables will be recorded for all collected AEs:

- Onset date of the health issue or start of the worsening of the issue
- Intensity (mild, moderate, severe)
- Duration of the issue (estimated number of days)
- Outcome (resolved, unresolved, fatal, unknown)
- **CCI**
- Treatment received for the issue
- Seriousness (SAE, non-SAE)
- Causality

SCI

• Adverse event of special interest details (if relevant)

If the participant indicates an AE may be related to COVID-19 or if they received a diagnosis for COVID-19, they will be asked about any COVID-19 testing and results.

For additional details on AE definitions, management, and reporting, refer to Section 10.

8.4.3.2 Pregnancy Outcomes

Data will be collected for pregnancy outcomes and infant outcomes. For pregnancy outcomes, events within the AESI medical concept "Pregnancy outcome – Maternal" will be collected, including spontaneous abortions, still births, and preterm births. For infant outcomes, events within the AESI medical concept "Pregnancy outcome – Neonates" will be collected, including major congenital malformations and small for gestational age.

8.4.3.3	CCI
CCI	
8.4.3.4	CCI
CCI	
	as per the data collection schedule described in Table 3.
CCI	

8.5 Data Sources

8.5.1 Vaccination Sites

Vaccination sites will provide participants with a vaccination card/record that includes the participant's name, the vaccine dose date, and the batch/lot number.

8.5.2 Participants: Study App, Web Portal, and Call Centre

Participants will record their baseline characteristics and will report post-vaccination outcomes using the study app, web portal, or call centre. Generally, participant inputs will be responses to the timed study questionnaires but can also include documentation like a photo of their vaccination card. A proxy may assist with any enrolment, reporting, or follow-up actions on behalf of the participant (Section 8.5.3). Participants can switch data reporting methods during the study but will be encouraged to use a consistent method for answering the health-related quality of life questionnaires.

The study app can be downloaded by participants to their mobile device. At vaccination sites with a study research coordinator present, the coordinator may assist participants with downloading and using the app. In mobile units where a study research coordinator might not be present, or when a participant decides to enrol later remotely, vaccine study cards will be available that will provide similar instructions.

The web portal will be accessible from any internet-connected computer and will allow users to securely login to a website and perform study-related activities.

The call centre will be toll-free. In some locations, it will be available 24 hours/day and 7 days/week. In locations where the call centre is not 24/7, it will be available weekdays during business hours and have an out of hours voicemail with call-back support. For participants that choose to communicate by telephone call, the call centre team will enter their responses into the digital platform. Accordingly, all patient-reported data will be integrated in the digital platform, regardless of the reporting method.

8.5.3 Emergency Contacts and Proxies

At enrolment, all participants will be asked to provide information for an emergency contact. In the case of non-response from a participant, the emergency contact would be contacted to confirm if the participant is unavailable due to incapacity or death.

If a participant is unable to directly provide any requested information, a proxy can do so on the participant's behalf. Participant proxies may include a caregiver, family member, or other trusted individual. The proxy will enter the participant's data into the app or web portal on the participant's behalf.

A proxy may act on the participant's behalf throughout the study or may step in if needed due to the participant's illness or incapacity. If a proxy is needed at the onset of the study, the participant can identify the proxy during enrolment. Instructions for the proxy on how to report outcomes on behalf of the participant will be available from a research coordinator or study information brochure.

Participants will be asked to only nominate a single proxy and will be asked for the appropriate permission for the proxy to handle their medical data for the limited purpose of assisting with data collection for this study, in accordance with local rules.

8.5.4 Medical Records

Medical records (paper or electronic) will be used to confirm comorbidities and medications at baseline and to follow up AEs reported during the study. Medical records will also be used to confirm pregnancy, birth, and infant outcomes. For all SAEs, AESIs, and medically-attended AEFIs, medical records will be requested from the participant's HCP.

